6.10. Management of virological breakthrough

Definition: Virological breakthrough is defined as a $> 1\text{-log}_{10}$ IU/mL increase in HBV DNA level from nadir in a participant with an initial virological response or redetection of HBV DNA after becoming undetectable, and will be confirmed on re-testing 4 weeks later in a participant with either an initial or partial virological response and who has been compliant with study medications.

- Virologic breakthrough is considered a treatment failure.

Management algorithm if virological breakthrough
6.10.1. Reinforce compliance. The importance of compliance with study medication will be reinforced with study participants at each visit.

6.10.2. Resistance testing will be performed but will not be used to guide decisions (as results will not be available in real-time). Participants meeting the definition for virologic breakthrough on repeat testing will stop all treatment.

6.10.3. Participants will be assessed at weeks 4, 12, 24, and 48 post-discontinuation.

6.11 Management algorithm for participants with ALT flare during the treatment phase

6.11.1. If ALT values increase to ≥ 300 U/L for males and ≥ 200 U/L for females, retest the hepatic panel within 4 weeks. Continue testing of hepatic panel every 4 weeks as long as the ALT remains >300 U/L for males and >200 U/L for females.

6.11.2. If ALT values decline below these levels, the frequency of testing the hepatic panel can return to the usual schedule.

6.11.3. Participants will remain on treatment until week 48 unless:

- i. there are signs of clinical decompensation or
- ii. total bilirubin ≥ 2.0 mg/dL and direct bilirubin ≥ 1.0 mg/dL or
- iii. ALT >450 U/L for males or >300 U/L for females for more than 12 weeks

Participants meeting any of these criteria will continue to be followed in the study but with any subsequent management at the discretion of the study physician.

6.12. Management algorithm for participants with ALT elevation during the follow-up phase (weeks 48-96)

6.12.1. If ALT increases to >300 U/L for males and >200 U/L for females, retest the hepatic panel in 4 weeks. Continue testing of hepatic panel every 4 weeks as long as the ALT >300 U/L for males and >200 U/L for females.

6.12.2. If ALT decline below these levels, the frequency of testing the hepatic panel can return to the usual schedule.

6.12.3. For participants with ALT persistently >150 U/L in males and >100 U/L in females for ≥ 24 weeks and HBV DNA $\geq 10,000$ IU/mL, they are eligible for retreatment with entecavir (up to one year or by December 31, 2015 (whichever comes first), or peginterferon alfa-2a or both drugs for one year if desired by participants and provider.

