5.1 Dosage and administration

Treatment Entecavir 0.5 mg daily orally for 48 weeks plus peginterferon alfa-2a 180 µg subcutaneously (sq) weekly during weeks 9-48 of treatment. After treatment discontinuation, follow-up off treatment will be for 48 weeks.

Participants will be instructed to take one tablet of entecavir daily on an empty stomach at least 2 hours prior to or after meals. Participants will be instructed to take 180 µg of peginterferon alfa-2a subcutaneously once weekly. The participant will be instructed to inject the peginterferon alfa-2a on the same day each week.

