6.4. On-treatment assessments

After starting treatment, visits will occur at weeks 8, 12, 16, 20, 24, 30, 36, 42, and 48. Each visit will include assessment of compliance, adverse events reporting, vital signs, weight, symptoms evaluation, record of concomitant medications, and blood testing as detailed in Schedule of Events (Appendix I). Participants will be dispensed study medications.

1. At the Week 8 visit, peginterferon alfa-2a will be provided to subjects with instructions on its use, including education on self-injection, if appropriate. Subjects will have a limited clinical evaluation as well as blood and urine tests.

2. Pregnancy test will be done in women with reproductive potential at each visit until the end of treatment.
3. Depression assessment will occur at weeks 8, 12, 24, 36 and 48.
4. QOL assessments will occur at day 0, weeks 8 and 48. Health behaviors will be included at day 0 and week 48.
5. Fatigue questionnaire will occur at day 0.
6. CBC (with differential), hepatic panel (ALT, AST, total bilirubin), renal panel (Cr, CrCl) and HBV DNA quantitation at each visit.
7. TSH at week 12, 24, 36 and 48.
8. Albumin, alkaline phosphatase, glucose and total protein will be obtained at week 48
9. HBeAg at weeks 8, 12, 24, 36 and 48.
10. HBsAg at week 48.
11. Blood samples for serum/plasma at each visit.
12. HBsAg and HBeAg quantification at each visit.
13. Anti-HBs/HBe will be done at day 0 and week 48. Also at the next visit if HBsAg/HBeAg becomes negative.

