6.8 Stopping rules

Therapy will only be stopped for the following indications:

- Grade IV toxicity (except hematologic, see appendix III.)
- Death
- Pregnancy

- Non-response per section 6.9.
- Virologic breakthrough per section 6.10.
- Hepatic decompensation defined by:
 - Total bilirubin ≥ 2.0 mg/dL and direct bilirubin ≥ 1.0 mg/dL
 - Any clinical measure of decompensation
- Participant refusal to continue treatment

Participants who discontinue treatment due to grade IV toxicity or hepatic decompensation will continue to be followed until these events are resolved or stabilized, according to the post-treatment follow-up schedule. Managing these participants including more frequent assessments and alternative treatment will be at the discretion of the investigator.

Participants who become pregnant while receiving treatment will stop treatment and subsequent management will be at the discretion of the investigator. The outcome of the pregnancy will be recorded.

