Appendix I: Schedule of events for treated participants

Phase of Study	Screening				Treatment										Follow-up			
	-28 to -52	-6 to -28	up to -6	0 ¹	8	1 ²	1 ²	6	2 ⁰	2 ⁴	3 ⁰	3 ⁶	4 ²	4 ⁸	5 ²	6 ⁰	7 ²	9 ⁶
Weeks of Study	-28 to -52	-6 to -28	up to -6	0 ¹	8	1 ²	1 ²	6	2 ⁰	2 ⁴	3 ⁰	3 ⁶	4 ²	4 ⁸	5 ²	6 ⁰	7 ²	9 ⁶
Informed consent			X															
Medical history			X															
Physical exam			X	X	X	X	X	X	X	X	X	X	X	X				X
Drug dispensing				X	X	X	X	X	X	X	X	X	X					
Adherence assessment/ Clinical evaluation including AEs, concomitant meds				X	X	X	X	X	X	X	X	X	X	X	X	X	X	X
Anthropometric measures					X										X			X
Questionnaires (QOL)					X	X									X			X
Health behaviors					X										X			X
Depression assessment			X		X	X				X		X		X		X		X
Symptom questionnaire					X	X	X	X	X	X	X	X	X	X	X	X	X	X
Fatigue questionnaire					X													X
CBC, including platelets and differential ²			X	X	X	X	X	X	X	X	X	X	X	X	X	X	X	X
Hepatic tests (AST, ALT, and bilirubin; albumin and ALKP day 0 and weeks 48 and 96 only) ³	X ⁴	X ⁴	X	X	X	X	X	X	X	X	X	X	X	X	X	X	X	X
Other chemistries (glucose, total protein)			X												X			X
TSH			X			X				X		X		X		X		X
Renal tests (Creatinine and CrCl calculated MDRD)			X	X	X	X	X	X	X	X	X	X	X	X	X	X	X	X
Urinalysis			X	X	X										X			X
PT/INR			X	X											X			X
AFP			X															
Pregnancy test (urine or blood) ⁵			X	X	X	X	X	X	X	X	X	X	X	X				

Phase of Study	Screening				Treatment												Follow-up			
	-24 to -52	-6 to -24	up to -6	0 ¹	8	1	1	2	2	3	3	4	4	5	6	7	9			
Weeks of Study				0 ¹	8	1	1	2	0	0	6	2	8	2	0	2	6			
HBsAg				X										X			X	X		
HBsAg quant					X	X	X	X	X	X	X	X	X	X	X	X	X	X		
HBeAg				X	X	X	X			X		X		X		X	X	X		
HBeAg quant					X	X	X	X	X	X	X	X	X	X	X	X	X	X		
Anti-HBe ⁶					X									X				X		
Quant HBV DNA	X ⁴			X	X	X	X	X	X	X	X	X	X	X	X	X	X	X		
Anti-HBs ⁶					X									X				X		
HBV genotype and subtype ⁷					X															
HBV precore/BCP					X													X		
Antiviral drug resistance mutation testing ⁹⁸					X										X					
Anti-HCV ⁹					X															
Anti-HDV ⁹					X															
Anti-HIV					X										X					
Abdominal imaging ¹⁰					X						X				X			X	X	
Plasma/serum banking ¹¹					X	X	X	X	X	X	X	X	X	X	X	X	X	X		
DNA Banking ¹²					X															

¹. Day 0 is the Baseline visit, and start of study drug.

². CBC to include differential count up to week 48.

³. If total bilirubin elevated, obtain direct bilirubin at next blood draw.

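### The bilirubin stopping criterion needs a direct bilirubin that Appendix I footnote 3 defers to the next draw, so applying it can be delayed by up to 4 weeks in an on-treatment ALT flare

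*Combined protocol and SAP*

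**What the plan says.** Section 6.8 lists hepatic decompensation among the reasons to stop therapy. Its laboratory form is "Total bilirubin ≥ 2.0 mg/dL and direct bilirubin ≥ 1.0 mg/dL"; clinical evidence of decompensation is the alternative. Section 6.11.3 repeats the bilirubin pair as criterion ii for a flare. There the default is to continue: "Participants will remain on treatment until week 48 unless" one of three criteria is met (clinical signs, the bilirubin pair, or a prolonged high ALT).

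Section 6.11.1 asks for a repeat hepatic panel within 4 weeks of the flare, then: "Continue testing of hepatic panel every 4 weeks as long as the ALT remains >300 U/L for males and >200 U/L for females". Section 6.4 item 6 gives the content of the panel: "hepatic panel (ALT, AST, total bilirubin), renal panel (Cr, CrCl) and HBV DNA quantitation at each visit". Direct bilirubin is not in it. Appendix I footnote 3, attached to the hepatic tests row, supplies the missing test: "If total bilirubin elevated, obtain direct bilirubin at next blood draw".

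On synthetic function, section 6.4 item 8 says: "Albumin, alkaline phosphatase, glucose and total protein will be obtained at week 48". The Appendix I row agrees, giving albumin at day 0 and weeks 48 and 96. PT/INR is scheduled at screening, at day 0, apparently at week 48, and at week 96. The week 48 position is inferred from column alignment, because the table is broken in the text available.

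**The concern.** A criterion that joins two measurements can be applied only when both are available. The plan collects one at every visit and the other one draw after the first becomes abnormal. When total bilirubin rises quickly, the sample that meets the first half of the criterion carries no result for the second half, and the participant stays on treatment by default until the next draw.

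What is at stake is the promptness of a safety rule that the plan itself sets, in a population for which section 1.3 says there are no earlier treatment studies in adults. Safety is a primary endpoint. The efficacy endpoint and its estimate are not touched.

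**Working it through.** The plan gives no figure on this point to reproduce. The check sets the test orders beside the criterion and then counts the longest wait.

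**1. Inputs.**
- Criterion: total ≥2.0 and direct ≥1.0 mg/dL (6.8, 6.11.3 ii).
- Panel: ALT, AST, total bilirubin (6.4 item 6).
- Direct bilirubin: next draw after an elevated total (Appendix I footnote 3).
- On-treatment visits: weeks 8, 12, 16, 20, 24, 30, 36, 42, 48 (6.4).
- Flare retest: within 4 weeks, then every 4 weeks (6.11.1).
- Peginterferon: "weekly during weeks 9-48 of treatment" (5.1), first supplied at the week 8 visit (6.4 item 1).

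**2. Two cases, following the text as written.**

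| Total at prior draw | Total at current draw | Direct bilirubin due | Can the criterion be judged now? |
|---|---|---|---|
| Elevated, below 2.0 | ≥2.0 | Current draw | Yes, delay 0 |
| Not elevated | ≥2.0 | Next draw | No, wait one draw |

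The table assumes that a total counts as elevated at some level below 2.0 mg/dL; footnote 3 states no cut-off.

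**3. Length of the wait.**
Gaps between scheduled visits from week 8 to week 48: 4, 4, 4, 4, 6, 6, 6, 6 (sum 40 weeks).
In a flare, wait ≤ min(gap to next visit, 4 weeks):
- weeks 8 to 20: min(4, 4) = 4 weeks
- weeks 24 to 42: min(6, 4) = 4 weeks

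The ceiling in a flare is therefore 4 weeks, or up to 4 weekly peginterferon injections if the dose is not held. Section 6.8 also applies outside a flare. There the ceiling is the scheduled gap: 4 weeks up to week 24 and 6 weeks after it. That second figure does not describe the flare case. All of these are maxima, because an earlier draw is allowed.

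**4. Number affected.** The documents give no rate for flares or for rapid bilirubin rises, so the count out of 40 cannot be estimated and may be 0.

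**5. PT/INR and albumin.** Visits after day 0 and before week 48: 8, 12, 16, 20, 24, 30, 36, 42 = 8 visits. The protocol text schedules PT/INR or albumin at 0 of these 8. Seven of them (weeks 12 to 42) fall within peginterferon treatment. Exclusion 2 uses INR >1.5 and albumin <3.5 g/dL as markers of decompensation at entry, but neither is named in 6.8 or 6.11.3.

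**The case against.** **Sites would obtain direct bilirubin anyway.** Exclusion 2 uses direct bilirubin >0.5 mg/dL, yet the screening list in 6.2 names only total bilirubin, so the test lists are evidently not exhaustive. A site might therefore measure direct bilirubin whenever a criterion calls for it. This is a fair inference, and nothing forbids it. But footnote 3 speaks directly to timing and says the next draw, so a site that follows the text has no instruction to do it sooner.

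**Other routes to stopping exist.** Clinical signs of decompensation stop treatment without any direct bilirubin. Grade IV toxicity is a separate stopping reason. Section 7.2 item 5 and Appendix III let the physician reduce peginterferon on judgement, and potential drug-induced liver injury is handled as a serious adverse event. All of this stands. Only the laboratory criterion is delayed, and the treatment given during the wait need not be at full dose.

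**The circumstances are narrow.** Total bilirubin must pass from not elevated to at least 2.0 mg/dL between consecutive draws, with no clinical sign and no early recall. Entry rules (INR, albumin, direct bilirubin and platelet limits, and biopsy above age 50) make low hepatic reserve unlikely. This also stands, and it is why the point is minor.

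**A stronger reading on synthetic function.** A reader might infer that the absence of PT/INR and albumin at weeks 8 to 42 leaves the stopping rules unworkable. The documents do not support that. Neither test is an on-treatment stopping criterion, and the physician may order both. The Manual of Operations, to which section 9.1 refers for management guidelines, was not available and may add tests. That part is only an optional suggestion.

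**Conclusion.** The point holds as a cheap improvement of minor severity. As written, the plan can delay its own bilirubin stop by one draw: at most 4 weeks under the flare schedule, and not at all if total bilirubin was already elevated at the prior draw. The number affected is unknown and may be 0 of 40. No efficacy estimate changes.

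A reader might go further and conclude that sections 6.8 and 6.11 contradict Appendix I, or that participants with decompensation must be kept on drug for weeks. Neither follows. The criterion can be applied one draw later, clinical signs and physician discretion operate in the meantime, and an earlier recall is allowed.

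The verdict rests on three assumptions: that sites follow footnote 3 literally, that a total below 2.0 mg/dL can count as elevated, and that the Manual of Operations does not already require the test on the same sample.

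**What to change.** Change Appendix I footnote 3 to: *If total bilirubin is elevated, measure direct bilirubin on the same sample.* In section 6.11.1, name direct bilirubin as part of each flare retest. It would help to state the cut-off for an elevated total.

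Optional: add PT/INR and albumin to the flare retests, to inform the judgement of clinical decompensation that 6.8 and 6.11.3 i already leave to the physician. No automatic INR or albumin stopping rule should be added.

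Cost: two short text edits and a few extra direct bilirubin assays. The optional part adds a coagulation tube and an albumin assay at retests in participants who flare. No stopping threshold changes, and neither the sample size nor the analysis is affected.

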6.13. Participants previously randomized to control group

Participants enrolled in this trial prior to amendment 7.0 of this protocol who were randomized to the control (no treatment) group will be offered treatment if they still meet the entry criteria for this trial (i.e. HBV DNA and ALT results from the most recent IT trial visit meet the inclusion and exclusion criteria listed in sections 4.1 and 4.2), and are willing to receive treatment. These participants will be reconsented prior to starting treatment and follow the visit schedule and assessment beginning with baseline (Day 0) visit.

Participants who no longer meet entry criteria for this trial or are not interested in receiving treatment will complete a Termination Visit at the next scheduled visit for the control (no treatment) group. The procedures to be followed for this Termination Visit will be those specified for the Week 48 visit.

7. Adverse events and toxicity management

7.1. Managing peginterferon alfa-2a side effects

Common side effects of peginterferon alfa-2a include influenza-like symptoms, particularly with the first few injections, fatigue, neuropsychiatric symptoms such as depression and reduction in white blood cell counts and platelet counts. Hyper- or hypothyroidism has been noted to occur in up to 5% of patients receiving peginterferon alfa-2a.

Some rare but potentially serious side effects include:

- neuropsychiatric complications, which may include suicide, suicidal ideation and severe depression
- serious and severe bacterial infections, some fatal have been reported during treatment with peginterferon alfa-2a
- pancreatitis
- interstitial pneumonitis, fatal cases have been reported with peginterferon alfa 2a use

Other possible but uncommon adverse events associated with peginterferon alfa-2a include:

- development or exacerbation of existing autoimmune disorders such as rheumatoid arthritis, systemic lupus erythematosus, idiopathic thrombocytopenic purpura, psoriasis etc
- other pulmonary disorders including dyspnea, pulmonary infiltrates, and sarcoidosis
- exacerbations of inflammatory bowel disease
- eye disorders, including decrease or loss of vision, retinal hemorrhages
- hypersensitivity including sometimes severe skin reactions in the spectrum of Stevens Johnson syndrome

7.1.1. Managing depression

When possible, the CES-D will be used along with the investigators judgment, to screen participants for depression at the screening visit (within 6 weeks of the baseline visit) and to monitor for onset or worsening of symptoms during the treatment and follow-up phases visits in all participants (See Schedule of Events). If a participant has a CES-D score >15 at the screening visit (within 6 weeks of the baseline visit), evaluation by a mental health provider should be considered before enrollment (start of treatment). During the treatment phase, if a participant has a CES-D score >15 , the investigator will determine whether referral to a mental health provider is indicated.

If the management of the depression is not successful after eight weeks or if the participant develops suicidal or homicidal ideation, the peginterferon alfa-2a will be stopped but entecavir continued until the end of the treatment period (see section 7.5.4) and the participant will be referred to a mental health provider.

7.2. Peginterferon alfa-2a dose reduction guidelines

Factors that may lead to a reduction in the dose of peginterferon alfa-2a include:

1. Disabling symptoms, which, in the opinion of the investigator, are related to Peginterferon alfa-2a treatment and prevent the participant from performing his/her occupation or daily tasks.
2. A rash consistent with allergic reaction or vasculitis.
3. Reductions in the platelet count according to the guidelines in Appendix III.
4. A reduction in neutrophil count according to the guidelines in Appendix III.
5. Any adverse reaction, which, in the opinion of the study physician, places the participant at increased risk.

The dose of study medications may be decreased due to adverse events or laboratory abnormalities. In most instances the dose of peginterferon alfa-2a will be reduced in graduated steps as follows:

- Level 1 decrease from 180 μ g to 135 μ g
- Level 2 decrease from 135 μ g to 90 μ g
- Level 3 decrease from 90 μ g to 45 μ g

For participants who require a downward dose adjustment for neutropenia or thrombocytopenia, laboratory values should be repeated, if practical, prior to the next dose of peginterferon alfa-2a to confirm the result and dictate the course of action. Participants who remain with a neutrophil count below 500/mm³ (but above 250/mm³) or a platelet count below 50,000/mm³ (but above 25,000/mm³) should receive stepwise dose reductions until levels of neutrophils and platelets are $\geq 500/\text{mm}^3$ or $\geq 50,000/\text{mm}^3$, respectively, or until a dose of 45 μ g of peginterferon alfa-2a is reached.

7.2.1. Guidelines for subsequent peginterferon dose adjustments

Once a participant's dose has been decreased for laboratory abnormalities or adverse events, the study physician may attempt to increase the dose back to or toward the previous stable level according to the following guidelines:

1. The event or circumstance responsible for the dosage adjustment has resolved or improved;
2. The participant has been at the lower dose for ≤ 4 consecutive doses;
3. The participants had ≤ 6 total doses administered at the lower level during the entirety of the treatment period.

If four or more consecutive doses of peginterferon alfa-2a are held or otherwise not administered (i.e., the participant has not received test medication for more than 28 days), the participant will be considered intolerant of the test medication or non-compliant, whichever is more appropriate to the clinical situation. In such cases, the study physician will discontinue peginterferon alfa-2a but entecavir treatment will continue (see section 7.5.4).

Every attempt will be made to keep participants on treatment with peginterferon alfa-2a on therapy by dose reduction. The use of hematological growth factors during the study will not be allowed.

7.2.2. Peginterferon alfa-2a dosing and creatinine clearance (CrCL)

Creatinine clearance will be calculated in all participants prior to initiating therapy and at each study visit. The peginterferon alfa-2a dose does not require adjustment unless the patient is on dialysis. However, in this study, peginterferon alfa-2a will be discontinued if CrCl is ≤ 30 ml/min to be consistent with criteria for entecavir discontinuation (see below).

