4.2. Exclusion criteria

- 1. History of hepatic decompensation, including but not limited to ascites, variceal bleeding, or hepatic encephalopathy.

2. Evidence of decompensated liver disease prior to or during screening, including direct bilirubin >0.5 mg/dL, INR >1.5, or serum albumin <3.5 g/dL.
3. Platelet count <120,000/mm³, hemoglobin <13 g/dL (males) or <12 g/dL (females), absolute neutrophil count < 1500 /mm³ (<1000/mm³ for African-Americans) at the last screening visit.
4. Previous treatment with medications that have established activity against HBV including, but not limited to, interferon and nucleos(t)ide analogs ≥24 weeks. Patients with <24 weeks of prior HBV treatment and a wash-out period >24 weeks are not excluded. Brief and episodic use of famciclovir or valacyclovir for herpes infection is not exclusionary.
5. Known allergy or intolerance to any of the study medications.
6. Females who are pregnant or breastfeeding.
7. Females of childbearing potential unable or unwilling to use a reliable method of contraception during the treatment period.
8. Renal insufficiency with calculated creatinine clearance <50 mL/min at the last screening visit.
9. History of alcohol or drug abuse within 48 weeks of the baseline visit.
10. Previous liver or other organ transplantation including engrafted bone marrow transplant.
11. Any other concomitant liver disease, including hepatitis C or D. Non-alcoholic fatty liver disease (NAFLD) with steatosis and/or mild to moderate steatohepatitis is acceptable but NALFD with severe steatohepatitis is exclusionary.
12. Presence of anti-HDV or anti-HCV (unless HCV RNA negative) in serum on any occasion in the 144 weeks prior to the baseline visit.
13. Presence of anti-HIV (test to be completed within 6 weeks prior to the baseline visit).
14. Pre-existing psychiatric condition(s), including, but not limited to:
 - a. Current moderate or severe depression as determined by the study physician
 - b. History of depression requiring hospitalization within past 10 years
 - c. History of suicidal or homicidal attempt within the past 10 years
 - d. History of severe psychiatric disorders including, but not limited to schizophrenia, psychosis, bipolar disorder as determined by a study physician.

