7.3.2. Entecavir and renal function

Entecavir dosing is based upon CrCL: Creatinine clearance will be calculated for all participants prior to initiating therapy and at each study visit to determine Entecavir dose.

- Participants whose calculated creatinine clearance decreases to <50 ml/min should have this value confirmed within 72 hrs.
- Entecavir may be continued if the CrCL is ≥30-50 ml/min at the adjusted dose of 0.5 mg every 48 hours.
- Entecavir will be discontinued if the CrCL is <30 ml/min.

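### Three dose-management cut-offs disagree with their companion passages at exact boundary values: creatinine clearance 30, creatinine clearance 50 and platelets 50,000

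*Combined protocol and SAP*

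**What the plan says.** **Creatinine clearance 30.** Section 7.2.2 sets the renal stopping rule for peginterferon and gives its reason: "peginterferon alfa-2a will be discontinued if CrCl is ≤ 30 ml/min to be consistent with criteria for entecavir discontinuation". It points forward to the entecavir criteria. Those are in Section 7.3.2: "Entecavir will be discontinued if the CrCL is <30 ml/min", and "Entecavir may be continued if the CrCL is ≥30-50 ml/min at the adjusted dose of 0.5 mg every 48 hours".

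**Platelets 50,000.** Section 7.2 lists platelet falls as a ground for dose reduction and refers to Appendix III for the rule. It then says that participants who remain with "a platelet count below 50,000/mm³ (but above 25,000/mm³) should receive stepwise dose reductions", and that this goes on until the count is at least 50,000/mm³ or the lowest dose step is reached. Part b of Appendix III gives no change only for counts strictly above 50,000. It assigns 25,000 to 50,000 to an initial one-step reduction.

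**Creatinine clearance 50.** Item 8 of Section 4.2 excludes "Renal insufficiency with calculated creatinine clearance <50 mL/min at the last screening visit", so a value of 50 is eligible. Section 7.3.2 asks for a confirmatory value within 72 hours only when clearance falls below 50. Its adjusted-dose band nevertheless runs up to and includes 50. Section 5.1 gives the general entecavir regimen as daily.

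**Renal measure.** The schedule in Appendix I has a row "Renal tests (Creatinine and CrCl calculated MDRD". Sections 4.2, 7.2.2 and 7.3.2 state their cut-offs as creatinine clearance in mL/min and name no equation.

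**The concern.** These are operative instructions, not background. Section 9.1 relies on Section 7 for the dose-adjustment and discontinuation guidelines and has protocol adherence reported quarterly. Safety is a primary endpoint, and Section 8.1.1 plans separate summaries of adverse events that led to permanent discontinuation or temporary interruption of study drug.

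If two passages treat one laboratory value differently, two sites can act differently and each can cite the protocol. An adherence report then has no single standard for that value. At a clearance of 30 the problem takes another form. Section 7.2.2 gives a reason for its own rule, and the rule does not achieve it, so a reader cannot tell whether the split between the two drugs was intended.

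**Working it through.** No sample size, power or error rate is involved, and the plan states no figure to reproduce. The check is to apply each rule as written at its cut-off and just either side.

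**Step 1. Renal rules.** Inputs: peginterferon stops at ≤30 (7.2.2); entecavir stops at <30 and is in the adjusted band from 30 to 50 inclusive (7.3.2); confirmation is asked for at <50 (7.3.2); exclusion at screening is at <50 (4.2, item 8).

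| Clearance (mL/min) | Peginterferon, 7.2.2 | Entecavir, 7.3.2 | Confirmation, 7.3.2 | Screening, 4.2 |
|---|---|---|---|---|
| 29.9 | stop | stop | yes | excluded |
| 30 | stop | continue, adjusted band | yes | excluded |
| 30.1 | continue | continue, adjusted band | yes | excluded |
| 49 | continue | continue, adjusted band | yes | excluded |
| 50 | continue | adjusted band | no | eligible |
| 51 | continue | general regimen | no | eligible |

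The two stopping rules differ at 30 and nowhere else. At 50 the adjusted band applies, although the same value passes eligibility and does not trigger confirmation. The rules that treat values below 50 as reduced function and the rule that also counts 50 part company at that value only.

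**Step 2. Platelet rules, for a participant already under dose adjustment.** Inputs: 7.2 reduces when the count is above 25,000 and below 50,000, and ends at ≥50,000; Appendix III reduces from 25,000 to 50,000 and makes no change only above 50,000.

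| Platelets (/mm³) | Section 7.2 | Appendix III |
|---|---|---|
| 49,999 | reduce | reduce |
| 50,000 | target met, no further reduction | reduce |
| 50,001 | target met, no further reduction | no change |

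The texts differ at 50,000 only. The neutrophil rules are a useful comparison: at 499 both texts reduce, and at 500 Section 7.2 counts the target as met and Appendix III makes no change. The mismatch is therefore confined to the platelet row.

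**Step 3. How far participants start from these values.** Section 4.2 excludes platelets below 120,000, so reaching 50,000 needs a fall of at least 120,000 − 50,000 = 70,000/mm³. It excludes clearance below 50, so reaching 30 needs a fall of at least 50 − 30 = 20 mL/min from the screening value. The boundary at 50 needs no fall, since a person screened at exactly 50 is already on it. The documents give no distribution of renal function or platelet counts, so no expected number of participants can be calculated.

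**Step 4. Renal measure.** Appendix I is the only place in these passages that names a method. No passage gives the units of the MDRD result or says how it is to be set against cut-offs in mL/min. The mapping is left undefined, but the text contains no second method for it to contradict.

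**The case against.** The strongest reply is that a site would seldom be misled.

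- **At clearance 30** the two rules concern different drugs, and each drug has one instruction. A reader might infer that one result leads to two different doses depending on the section consulted. The documents do not support that. Section 7.5.4 also shows that the protocol accepts one drug continuing after the other stops for an adverse event. What stands is narrower: the reason given in 7.2.2 is not met at 30.
- **At platelets 50,000** a reader might infer opposite actions for any participant with that count. For a first result, 7.2 simply refers to Appendix III, so only one rule applies. The conflicting sentence in 7.2 covers participants who remain low after an adjustment. Appendix III also calls itself guidance and leaves room for investigator judgement. That narrows the conflict to when stepwise reduction ends, but it does not make the two texts agree.
- **At clearance 50** the daily regimen in 5.1 followed by a renal adjustment in 7.3.2 is a general rule with a specific exception, not a contradiction in itself. What stands is that the upper end of the adjusted band does not match the eligibility and confirmation limits.
- **On MDRD** a reader might infer that the label shifts every renal cut-off for every participant according to body size. The documents do not support this. They give no units for the MDRD result, name no competing equation and provide no body-size data. Any converted range would rest on outside assumptions.

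**Conclusion.** The point holds as three single-value inconsistencies: clearance 30 (7.2.2 against 7.3.2), platelets 50,000 during an ongoing dose adjustment (7.2 against Appendix III), and clearance 50 (4.2 and the confirmation rule against the adjusted band in 7.3.2). All three follow from the current text with no outside figure.

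The size is small. Each conflict concerns one reportable value. Few of the 40 participants are likely to meet one; that is a judgement from the entry limits, not a calculated rate. The efficacy endpoint, its confidence interval and the sample size are not affected. The case for acting is that these are safety instructions in a trial with safety as a primary endpoint, and that correcting them costs very little.

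The MDRD row needs clarification only, and no size of effect is claimed for it.

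**What to change.** Reconcile three pairs of passages so that each value leads to one action:

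1. Section 7.2.2 with 7.3.2 at a clearance of 30. Either make the two rules agree or remove the statement that they do.
2. Section 7.2 with Appendix III, part b, at a platelet count of 50,000.
3. Sections 4.2 (item 8) and 5.1 with 7.3.2 at a clearance of 50, including whether that value calls for confirmation.

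Which cut-off applies in each case is for the sponsor's clinicians to decide; this review takes no view.

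As a minor addition, Appendix I should state how the MDRD result and its units map to the mL/min cut-offs in 4.2, 7.2.2 and 7.3.2. If the sponsor chooses a calculation that needs body weight, it should confirm the source at screening: Section 6.4 lists weight for on-treatment visits, but the screening list in 6.2 does not name it.

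The cost is a few inequality signs or short phrases and one line in Appendix I, made in an amendment. The three boundary corrections need no new data and no change to the analysis.
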